5.2 Study Groups

This will be an open-label, single-arm study. All subjects who provide informed consent and are eligible for participation based on the inclusion and exclusion criteria will undergo bronchial thermoplasty with the Alair System.

A randomized controlled trial in the United States or Canada would be unethical and extremely difficult to recruit for, because Control group patients with severe persistent asthma would be required to refrain from both the Alair treatment and from other alternative treatment opportunities for a period of 5 years.

5.3 Study Subject Recruitment

All study subjects will be volunteers who meet the Inclusion/Exclusion criteria. Recruitment of study subjects will likely be from the pool of patients attending asthma clinics at the study sites in the United States and Canada. Referrals may also be sought from local physicians/general practitioners in the community who see and treat asthma patients in their practice. A total of 300 subjects will be enrolled in the study with up to 20% of the subjects to be enrolled in Canada.

5.4 Inclusion Criteria

Subjects will be included in the study if they meet the following Inclusion criteria:

1. Subject is an adult between the ages of 18 to 65 years.
2. Subject is able to read, understand, and sign a written Informed Consent to participate in the study and able to comply with the study protocol.
3. Subject has asthma and is taking regular maintenance medication that includes inhaled corticosteroid (ICS) at a dosage greater than 1000 μ g beclomethasone per day or equivalent, AND long acting β_2 -agonist (LABA) at a dosage of \geq 80 μ g per day Salmeterol or equivalent. Subjects may also be on the following medications in addition to the ICS and LABA:
 - a. Other asthma medications such as leukotriene modifiers, or anti-IgE, (Subjects on Xolair[®] must have been on Xolair for greater than 1 year).
 - b. Oral corticosteroids (OCS) at a dosage of up to, but not greater than 10mg per day.*.
4. Subject has a pre-bronchodilator FEV₁ of greater than or equal to 60% of predicted.
5. Subject is a non-smoker for 1 year or greater (if former smoker, less than 10 pack years total smoking history).
6. Subject is able to undergo outpatient (same day) bronchoscopy in the opinion of the investigator or per hospital guidelines.
7. Subject has at least 2 days of asthma symptoms in the last 4 weeks.
8. Subject has an AQLQ score during the baseline period of 6.25 or less.

* NOTE: Subjects on a dosage regimen of 20mg OCS every other day may be included as this is equivalent to an average daily dosage of 10mg.

5.5 Exclusion Criteria

Subjects will be excluded from the study if they meet any of the following Exclusion criteria:

1. Subject is participating in another clinical trial within 6 weeks of the Baseline Period involving respiratory intervention that could affect the outcome measures of this Study.
2. Over the last 7 days of a 4 week medication stable period, subject requirement for rescue medication use other than for prophylactic use for exercise exceeds an average of:
 - a. 8 puffs per day of short-acting bronchodilator, or
 - b. 4 puffs per day of long-acting rescue bronchodilator, or
 - c. 2 nebulizer treatments per day.

At the discretion of the Principal Investigator, subjects considered as unstable on baseline medications may have medications adjusted and re-evaluated after a 4 week medication stabilization period.
3. Subject has a post-bronchodilator FEV₁ of less than 65%.
4. Subject has a history of life-threatening asthma, defined by past intubation for asthma, or ICU admission for asthma within the prior 2 years.
5. Subject has 3 or more hospitalizations for exacerbations of asthma in the previous year.
6. Subject has had 4 or more infections of lower respiratory tract (LRTI) requiring antibiotics in the past 12 months.
7. Subject has had 4 or more pulses of systemic corticosteroids (tablets, suspension or injection) for asthma symptoms in the past 12 months.
8. Subject has a known sensitivity to medications required to perform bronchoscopy (such as lidocaine, atropine and benzodiazepines).
9. Subject has other respiratory diseases including emphysema, cystic fibrosis, vocal cord dysfunction, mechanical upper airway obstruction, Churg-Strauss syndrome, and allergic bronchopulmonary aspergillosis (asthma, immediate cutaneous reactivity to *A. fumigatus*, total serum IgE of >1000ng/mL, elevated specific IgE and IgG to *A. fumigatus* with or without evidence of central bronchiectasis).
10. Subject has segmental atelectasis, lobar consolidation, significant or unstable pulmonary infiltrate, or pneumothorax, confirmed on x-ray.
11. Subject currently has clinically significant cardiovascular disease, including myocardial infarction, angina, cardiac dysfunction, cardiac dysrhythmia, conduction defect, cardiomyopathy, or stroke.
12. Subject has a known aortic aneurysm.

13. Subject has significant co-morbid illness such as cancer, renal failure, liver disease, or cerebral vascular disease.
14. Subject has uncontrolled hypertension (>200mm Hg systolic or >100mm Hg diastolic pressure).
15. Subject has an implanted electrical stimulation device (e.g., a pacemaker, cardiac defibrillator, or deep nerve or deep brain stimulator).
16. Subject has coagulopathy (INR > 1.5).
17. Subject has any other medical condition that would make them inappropriate for study participation, in the Investigator's opinion.

5.6 Outcomes of Interest

Primary endpoint: The primary endpoint will be the proportion of subjects experiencing severe exacerbations during the subsequent 12-month (for Years 2, 3, 4, and 5) compared to the first 12-month after the Alair treatment.

Note: Severe exacerbation defined as worsening of asthma symptoms requiring use of systemic corticosteroids (tablets, suspension, or injection). For subjects already taking oral corticosteroids on a daily or alternate day basis, a severe exacerbation will be defined as a worsening of asthma symptoms requiring any increase in daily dose of systemic corticosteroids.

For consistency, courses of corticosteroids separated by 1 week or more will be treated as separate severe exacerbations.

Secondary endpoints: The secondary endpoints will include the following additional safety endpoints which will be evaluated annually through Year 5 following treatment with the Alair System:

- Rates of Severe exacerbations (exacerbations / subject / year)
- Respiratory adverse events* (rates of respiratory adverse events, and proportion of subjects with respiratory adverse events)
 - * A respiratory adverse event is defined as any sign, symptom, illness, clinically significant abnormal laboratory value, or other adverse medical event associated with the "Respiratory System" that appears or worsens in a subject during a clinical study, regardless of whether or not it is considered related to the procedure used as part of the protocol.
- Emergency room visits for respiratory symptoms (rates of emergency room visits and proportion of subjects with emergency room visits for respiratory symptoms)
- Hospitalizations for respiratory symptoms (hospitalizations/ subject/ year and the proportion of subjects with hospitalizations for respiratory symptoms)

- Respiratory Serious Adverse Events (detailed narratives will be provided for each event)
- Pre- and post-bronchodilator FEV₁

5.7 Patient Success Criteria

The primary statistical objective is to demonstrate that the proportion of subjects who experience severe exacerbations in the subsequent 12-month follow-up (for Year 2, Year 3, Year 4 and Year 5 [in 12-month periods]) is not statistically worse when compared with the proportion of the first 12-months, which begins 6-weeks after the last Alair treatment. This objective will be met if the upper 95% confidence limit of the difference in proportions (i.e., the subsequent 12-month proportion minus the first 12-month proportion) is less than 20%.

6.0 Statistical Plan

6.1 Statistical Methods

All statistical processing will be performed using SAS® software Version 9.1 or later unless otherwise stated.

6.2 Demographic and Baseline Characteristics

Demographic variables (age, gender, ethnicity, and race), and baseline clinical information (maintenance asthma medication doses, Pre- and Post-BD FEV₁, prior 12 month history of use of systemic corticosteroids (tablets, suspension, or injection) for asthma symptoms, emergency room visits and hospitalizations for respiratory symptoms) will be recorded.

Continuous variables will be summarized with sample size, mean, standard deviation, median, minimum and maximum. Categorical variables will be summarized with frequency counts and percentages.

Demographic and baseline clinical information will also be provided separately for the subsets of patients enrolled at sites in the United States and sites in Canada.

6.3 Primary Analysis

Point estimates and 95% confidence intervals for the proportion of subjects experiencing severe exacerbations during each of the 12-month evaluation periods will be provided. Additionally, the upper 95% confidence limit for the difference between the subsequent 12-month proportions and the first 12-month proportion will be calculated; in this analysis, each subsequent 12-month proportion would represent comparisons between the first-year proportion and the second-, third-, fourth-, and fifth-year proportions.

An upper 95% confidence limit of the difference between the subsequent 12-month proportions (for Years 2, 3, 4, and 5) compared to the first 12-month proportion is less than 20% will demonstrate that the proportions are not substantially worse during each of the subsequent evaluation periods.

The proportions of patients with severe exacerbations at each year will be calculated with the denominator as the number of patients who complete follow-up visits for that particular year. Patients who are lost to follow-up will be excluded from the analysis. The hypothesis testing (non-inferiority design) will be conducted using the proportions calculated as described above.

Final conclusions regarding the durability of effectiveness (beyond 1 year) will be based on completing the 5 year follow-up of all subjects who are still in the study at that time.

Inferential analysis of the subset of subjects enrolled at sites in the United States or in Canada may lack the statistical power to demonstrate that the proportions are not substantially worse during each of the subsequent evaluation periods. Descriptive statistics for the point estimates introduced above will be presented for each subset, however, the primary endpoint analysis of the upper 95% confidence limit of the difference between the subsequent 12-month proportions (for Years 2, 3, 4, and 5) compared to the first 12-month proportion will not be required for the subsets.”

Sensitivity analyses (conducted at 5 years)

- Compare patients who complete the 5 year follow-up with those who are lost to follow-up at 5 years regarding the baseline characteristics including demographics and medical information. The purpose of this analysis is to address whether the missing data observed over the course of study is missing at random and to address the validity of the primary analysis.
- The following three sensitivity analyses will use a test of hypotheses and/or computation of equivalent confidence limits will be based on the statistical methods (formulas) appropriate for matched pairs for proportions noted in Section 2.2 of J. NAM, *“Establishing Equivalence of Two Treatments and Sample Size Requirements in Matched Pairs Design”*, *Biometrics* 1997; 53: 1422-1430.
 - Conduct an adjusted worst-case analysis, which is an intent to treat analysis that imputes missing data using multiple imputations by reasons of loss to follow-up (e.g., due to treatment-related adverse events and/or lack of efficacy; or reasons not related to treatment)
 - Conduct hypothesis testing using the matched pair design, but with multiple imputations.
 - Conduct hypothesis testing using the matched pair design without multiple imputations.

6.4 Secondary Analyses

Descriptive statistics will be performed for the following parameters for each 12-month period starting 6 weeks after the last treatment bronchoscopy and reported as including means and 95% CI:

- Rates of severe exacerbations (exacerbations / subject / year)
- Respiratory adverse events (rates of respiratory adverse events, and proportion of subjects with respiratory adverse events)
- Emergency room visits for respiratory symptoms (rates of emergency room visits, and proportion of subjects with emergency room visits for respiratory symptoms)
- Hospitalizations for respiratory symptoms (rates of hospitalizations, and proportion of subjects with hospitalizations for respiratory symptoms)
- Respiratory Serious Adverse Events (detailed narratives will be provided for each event)
- Pre- and post-bronchodilator FEV₁

Descriptive statistics for the subset of subjects enrolled at sites in the United States or in Canada alone will be provided for each of the secondary endpoints, although no conclusions can be drawn from either subset because of the smaller sample sizes.

6.5 Safety Analysis

Adverse events will be reported for the short-term (Treatment Period) and for the long-term (Post-Treatment Period). The Treatment Period will be defined at the Day of 1st procedure bronchoscopy till 6 weeks after the last procedure bronchoscopy. The Post-Treatment Period will begin at the end of the Treatment Period i.e. at beginning at 6 weeks after the last procedure bronchoscopy. Annual visits will be based on a 52 week period beginning at 6 weeks after the last procedure bronchoscopy.

An adverse event is defined as any sign, symptom, illness, clinically significant abnormal laboratory value, or other adverse medical event that appears or worsens in a subject during a clinical study, regardless of whether or not it is considered related to the procedure used as part of the protocol.

All adverse events reported during the study will be listed, documenting course, severity, possible relationship to procedure, and outcome. Verbatim terms will be classified to preferred terms and system organ classes using the MedDRA dictionary. The preferred terms and system organ classes will then be tabulated by the treatment period and each year of follow-up. All reported adverse events will be summarized by the number of subjects reporting adverse events, system organ class, preferred term, severity, duration, and relationship to procedure.

In addition to the complete tabulation of adverse events for all subjects enrolled in the study, adverse events will also be tabulated separately for the subsets of subjects enrolled in sites in the United States and the sites in Canada.

6.6 Study Size and Sampling

Under the assumption that in the population of US subjects treated with the Alair System the proportion of patients that experience severe exacerbations will be 0.33 (33% of subjects) or less (based on data from AIR2 Trial (Protocol #04-02); 30.9%, 95% CI 24.2%, 37.7%), a sample size of 200 is adequate to demonstrate durability of the treatment effect at 5 years post-Alair treatment. Up to 300 subjects (minimum of 250 subjects) will be enrolled to achieve at least 200 evaluable study subjects, accounting for a 20% drop-out rate over 5 years.

nQuery Advisor Version 7.0 was used to form a basis for the sample size estimation. The "Two group test of equivalence in proportions (large equal n's)" procedure based on a one-sided test at alpha equal to 0.05 and a 20% delta was used to generate the powers presented in Table 1.

Table 1: Sample Size Calculation

Two group test of equivalence in proportions (large equal n's)										nQuery Advisor 7.0
	1	2	3	4	5	6	7	8	9	
Test significance level, α (one-sided)	0.050	0.050	0.050	0.050	0.050	0.050	0.050	0.050	0.050	0.050
Standard proportion, π_S	0.330	0.330	0.330	0.330	0.330	0.330	0.330	0.330	0.330	0.330
Equivalence limit difference, $\pi_T - \pi_S, \Delta_0$	0.200	0.200	0.200	0.200	0.200	0.200	0.200	0.200	0.200	0.200
Test expected proportion, π_T	0.330	0.340	0.350	0.360	0.370	0.380	0.390	0.400	0.410	
Expected difference, $\pi_T - \pi_S, \Delta_1$	0.000	0.010	0.020	0.030	0.040	0.050	0.060	0.070	0.080	
Power (%)	99	99	99	98	97	95	92	88	83	
n_s	250	250	250	250	250	250	250	250	250	
n_T	200	200	200	200	200	200	200	200	200	
Ratio: n_T / n_s	0.800	0.800	0.800	0.800	0.800	0.800	0.800	0.800	0.800	
$N = n_s + n_T$	450	450	450	450	450	450	450	450	450	

A minimum of 80% power was achieved for all situations wherein the subsequent year's assumed proportion of subjects with severe exacerbations was 41% or less.

Because of the length of the follow-up period (5 years following Alair-treatment) it is expected that there will be Loss-to-Follow-up. However, every reasonable effort will be made to retain the subjects in the study over this follow-up period and to limit Loss-to-Follow-up to be less than 20% at the 5 year follow-up (with an average yearly loss <5%).

The study will be conducted at a minimum of 15, and a maximum of 30 centers in the United States and Canada. Investigational centers will include both teaching and non-teaching institutions and will be selected based on criteria that will include geographic location, physician experience with performing bronchoscopy procedures, access to adequate number of patients with severe asthma (either from own practice or through a referral network with allergists), and appropriate personnel resources to adequately execute the study protocol and collect all required data.

6.7 Data collection and Follow-up schedule

The planned study visits are outlined in the Study Flow Chart shown in Figure 2.

All data will be collected using appropriately designed case report forms (CRFs/eCRFs). Information on adverse events, incidences of OCS pulses for worsening of asthma symptoms, emergency room visits for respiratory symptoms, and hospitalizations for respiratory symptoms will be actively solicited by an appropriately qualified member of the clinical study site team during quarterly telephone contacts or at time of in-office visits.

Daily diaries will not be used in this clinical study, and all information solicited from the study subjects will be based on recall since the last contact (maximum recall time of 3 months). Episodes of worsening of asthma symptoms requiring treatment with oral corticosteroids, emergency room visits and hospitalizations for respiratory symptoms are rare events and are readily recalled for immediate past periods of 3 month duration. This approach will be consistent with data collection methodology in the AIR2 Trial.

The following data will be collected at the specified visits/evaluations:

Enrollment

- Medical history (including maintenance asthma medications and history of respiratory infections)
- Occurrence of events in the 12 month period prior to study enrollment
 - Severe exacerbations (pulses of systemic corticosteroids (tablets, suspension, or injection) for asthma symptoms)
 - Emergency room visits for asthma symptoms
 - Hospitalizations for asthma symptoms
- Forced Expiratory Volume in 1 second: FEV₁ (pre- and post-bronchodilator)
- Physical examination (including body weight)
- Chest X-ray (Lateral and PA)
- Asthma Quality of Life Questionnaire (AQLQ)

Treatment Period (Day of 1st bronchoscopy till 6 weeks after 3rd/last bronchoscopy)

- Adverse events
- Emergency room visits for respiratory symptoms
- Hospitalizations for respiratory symptoms
- FEV₁ (pre- and post-bronchodilator)

Phone Contact at every 3 Months between Annual Visits

- Adverse events
- Severe exacerbations
- Maintenance asthma medications
- Emergency room visits for respiratory symptoms
- Hospitalizations for respiratory symptoms

Annual Visits at 1, 2, 3, 4 and 5 years from end of Treatment Period (6 week visit following 3rd/last bronchoscopy)

- Adverse Events
- Severe exacerbations
- Physical examination (including body weight)
- Maintenance asthma medications

- Emergency room visits for respiratory symptoms
- Hospitalizations for respiratory symptoms
- FEV₁ (pre- and post-bronchodilator)

All adverse events will be actively solicited by an appropriately qualified member of the clinical study site team at the time of follow-up evaluations. For the periods between scheduled study visits or telephone contacts, subjects will be encouraged to keep track of any adverse events, pulses of oral corticosteroids for worsening of asthma symptoms, emergency room visits for respiratory symptoms or hospitalizations for respiratory symptoms in a medical event log. Subjects will be trained to contact study site team in the event there is an emergency room visit or hospitalization due to respiratory symptoms.

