7.3.3 Evaluations at Enrollment (Baseline)

- Determine whether the subject's maintenance asthma medications are in accordance with conventional therapy utilizing inhaled corticosteroids and long-acting β_2 -agonists appropriate for the severity of the Subject's asthma.

Subjects who require a medication adjustment in order to optimize asthma control must undergo a 4-week medication stabilization period prior to performing enrollment evaluations. If the subject's maintenance asthma medications ARE in accordance with conventional therapy and subject has been on stable asthma medications for at least four weeks:

- Administer Asthma Quality of Life Questionnaire (AQLQ).
- Obtain detailed medical history, to include:
 - Gender
 - Race
 - Date of birth
 - Number of years diagnosed with asthma
 - History of allergies, to include allergy type and the time of year they are susceptible
 - History of respiratory infections in the 2 years prior to the study
 - Other significant illnesses
- Obtain history of asthma symptoms, exacerbations, and asthma medications, to include:
 - Number of emergency room visits for respiratory symptoms over the past 12 months
 - Number of hospitalizations for respiratory symptoms over the past 12 months
 - Number of pulses of systemic corticosteroids (tablet, suspension, or injection) for asthma symptoms over the past 12 months
 - Number of Intensive Care Unit (ICU) admissions for asthma symptoms over lifetime, and timing of each such admission
 - Changes in maintenance asthma medications, if any
- Perform pre-bronchodilator spirometry following a 12-hour abstinence from long-acting β_2 -agonist and a 4-hour abstinence from short-acting β_2 -agonists.
- Perform post-bronchodilator spirometry 15 minutes after the administration of 4 puffs (100 μ g per puff) of albuterol via a spacer.
- Perform the following evaluations:
 - Physical examination, including body weight, vital signs, pulse oximetry (SpO_2) and breath sounds.
 - Blood coagulation panel and Complete Blood Count (CBC)
 - Pregnancy test for female subjects of childbearing potential (a positive pregnancy test at this time will disqualify the subject from the study).
 - Obtain Chest X-rays – lateral and posterior anterior (PA) views. Chest X-rays performed within the last 4 months may be used.

- If all entry criteria have been met, enroll the subject and schedule their first bronchoscopy session.

NOTES:

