1. *If the subject has an exacerbation during the period of enrollment evaluations that is treated with oral steroids, wait at least 4 weeks following completion of the oral steroids, before proceeding with any further evaluations.*
2. *During the period between enrollment and the entire study period out to 5 years, all subjects should continue to take the same dose, route, and frequency of inhaled corticosteroids, LABA, and other maintenance asthma medications prescribed prior to enrollment. In the instance that medications are adjusted for patient safety, record any deviations from this specified medication usage in the subject's medical chart and on CRF/eCRFs during subsequent follow-up visits.*

Provide the following specific instructions to all subjects that are enrolled in the study:

1. It is important to complete all scheduled study visits and respond to telephone contacts by the research team.
2. It is important to contact the Investigator or the research team if the subject experiences worsening of their asthma symptoms beyond their normal level of symptoms.
3. It is important to seek medical attention between scheduled study visits if necessary.
4. For the periods between scheduled study visits or telephone contacts, subjects should be encouraged to keep track of any adverse events, pulses of oral corticosteroids for worsening of asthma symptoms, emergency room visits for respiratory symptoms or hospitalizations for respiratory symptoms in a diary or log. For any event, subjects' should note the date event occurred, any treatment that was used to address the event, and the date the event was considered resolved. This will aid in an unbiased recall of events.
5. These instructions should be reinforced during each contact with a study subject.

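### Follow-up solicitation and subject-log wording names only oral steroid pulses, narrower than the primary endpoint; any resulting under-capture would favour meeting the 20-point criterion

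*Protocol*

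**What the plan says.** The primary endpoint is the proportion of subjects with a severe exacerbation in each of Years 2 to 5 compared with Year 1. Protocol 5.6 and 8.1 and SAP 2.1 define the event as worsening asthma that needs systemic corticosteroids as tablets, suspension or injection. For subjects already on daily or alternate-day oral steroids it is "a worsening of asthma symptoms requiring any increase in daily dose of systemic corticosteroids". Such subjects can enrol: Protocol 5.4 allows "Oral corticosteroids (OCS) at a dosage of up to, but not greater than 10mg per day".

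The follow-up wording is narrower in these places:

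- The Protocol 6.7 sentence on active solicitation at quarterly calls and office visits names "incidences of OCS pulses for worsening of asthma symptoms".
- The 6.7 justification for relying on three-month recall refers to episodes treated with oral corticosteroids.
- The log instruction near the end of 6.7, and instruction 4 to subjects in 7.3.3, name "pulses of oral corticosteroids for worsening of asthma symptoms".

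Baseline history, by contrast, is asked by all routes: "Number of pulses of systemic corticosteroids (tablet, suspension, or injection) for asthma symptoms over the past 12 months" (7.3.3, with similar wording in the 6.7 enrolment list).

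Other provisions are wider. The 6.7 lists for quarterly calls and annual visits include severe exacerbations, maintenance asthma medications and adverse events. Sections 7.3.12 and 7.3.13 and Table 2 require exacerbations and asthma medication use to be reviewed at each contact. Instruction 4 in 7.3.3 also covers adverse events generally and asks the subject to note "any treatment that was used to address the event".

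**The concern.** The study uses no daily diary. Events come from recall over as long as three months, and 7.3.3 presents the log as the aid to unbiased recall. The only steroid use that the log names is an oral pulse. A subject given an injection in an office, or told to raise a maintenance oral dose for a few days, may not think of that as an oral pulse.

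SAP 6.4 makes the record of the drug decisive. An adverse event becomes a severe exacerbation only if it links to a qualifying medication record. If worsening asthma is reported but the injection or dose change is not, no endpoint event results.

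The success criterion is an upper confidence limit below 20 points for the later-year proportion minus the Year 1 proportion. Lost events pull both proportions towards zero and so pull a real worsening towards zero, which is the direction of the sponsor's conclusion. The planned missing-data work (Protocol 6.3 and the tipping-point analysis in SAP 2.1.3) deals with subjects who lack follow-up. It does not address events missed in subjects who have it.

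**Working it through.** **1. Each event type against each prompt**

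| Source | Oral pulse | Injection | Dose rise on maintenance oral steroid |
|---|---|---|---|
| Endpoint (5.6, 8.1) | named | named | named |
| 6.7 active-solicitation sentence | named | not named | not named |
| Log instructions (6.7, 7.3.3) | named | only as treatment of an event (7.3.3) | only as treatment of an event (7.3.3) |
| 6.7 call and visit lists | through the defined term | through the defined term | through the defined term, and maintenance medications |
| SAP 6.4 filter | oral class | listed intravenous text strings only | no rule stated |

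The prompts are inconsistent. The wider ones lower the risk of a missed event, but they do not put the two extra event types to the subject by name.

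**2. Reproducing the plan's power**

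Inputs from Protocol 6.6 and Table 1: Year 1 proportion 0.33, margin 0.20, n = 250 and 200, one-sided alpha 0.05.

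Power = Φ[(0.20 − (π_T − π_S))/SE − 1.645], with SE = √[π_S(1 − π_S)/250 + π_T(1 − π_T)/200].

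At π_T = 0.41: SE = √(0.0008844 + 0.0012095) = 0.0458, and Φ(0.12/0.0458 − 1.645) = 83.6%. Table 1 states 83%.

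For π_T from 0.33 to 0.41 the results are 99.8, 99.5, 99.1, 98.3, 97.1, 95.1, 92.4, 88.5 and 83.6%. Table 1 has 99, 99, 99, 98, 97, 95, 92, 88 and 83%. The formula reproduces the plan.

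**3. Effect of equal under-capture in both years**

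Let c be the share of subjects with a true event in a year who have at least one recorded. The observed proportions are cπ_S and cπ_T, so the observed difference is c times the true one. The values of c are assumptions; the documents give none.

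At the null boundary (33% versus 53%) with c = 0.95, the observed proportions are 31.35% and 50.35%, a difference of 19 points. SE = √(0.3135 × 0.6865/250 + 0.5035 × 0.4965/200) = 0.0459. Chance of passing = Φ(0.01/0.0459 − 1.645) = 7.7%.

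| c, both years | Observed difference | Chance of passing |
|---|---|---|
| 1.00 | 20.0 points | 5.0% |
| 0.98 | 19.6 | 6.0% |
| 0.95 | 19.0 | 7.7% |
| 0.90 | 18.0 | 11.4% |
| 0.80 | 16.0 | 22.7% |

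For scale, c = 0.95 would arise if 10% of subjects with an event had only injection or dose-increase events that year and half of those subjects were missed: 1 − 0.10 × 0.5 = 0.95. A subject who also had a recorded oral course still counts, so only subjects with no recorded qualifying event lower c.

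At a true 8-point worsening (33% versus 41%), c = 0.95 gives an observed 7.6 points, and the chance of passing goes from 83.6% to 86.3%. If there is no true change, equal under-capture leaves the difference at zero.

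**4. Limit of the calculation**

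SAP 2.1.3 uses an exact paired limit. The independent-samples formula is used here because it reproduces Table 1. With positive within-subject correlation the paired standard error is smaller, so the same shift counts for more. The documents give no correlation, so no paired figure is offered.

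**The case against.** The strongest reply is that follow-up as a whole does not ask only for oral pulses. The call and visit lists use the defined term, which 8.1 spells out with injections and dose increases. Maintenance medications are collected at every contact, which bears directly on subjects already taking oral steroids. Adverse events are actively solicited, and worsening asthma is one. The 7.3.3 log instruction asks for the treatment of any event. SAP 6.4 lists intravenous corticosteroid entries and mentions misspellings in the entered data, so non-oral steroids do reach the database. The case report forms and any call script are not in the documents, so their prompts cannot be judged. All of this stands, and it rules out reading the mismatch as a proven loss of events.

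A reader might also infer that the loss grows from Year 1 to Year 5, because injections and dose increases could become more common as asthma worsens. The documents do not support this. Call frequency, content and the three-month recall limit are the same in all five years, and no share of such events is given for any year. The result is sensitive to that assumption. With half of such cases missed, a constant 5% share understates a 33% versus 41% difference by 0.5 × 0.05 × (0.41 − 0.33) = 0.2 points. Only by letting the later-year share rise to 15% does this reach 0.5 × (0.15 × 0.41 − 0.05 × 0.33) = 2.25 points.

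The contrast with baseline should not be pressed either. Baseline history is descriptive, the primary test compares follow-up years with each other, and the baseline question itself does not ask about dose increases.

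What the reply leaves standing is that the sentence describing solicitation and the subject's memory aid are both narrower than the endpoint, with no stated reason.

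**Conclusion.** The mismatch is real and concerns the primary endpoint. It amounts to inconsistent prompting that could leave some injection-only or dose-increase-only cases unrecorded. Whether any are lost, and how many, cannot be determined from the documents.

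The direction is clear if capture is incomplete to the same degree in each year: a real worsening is understated and the 20-point criterion becomes easier to meet. Under assumed equal capture of 98% to 90%, the chance of passing at the null boundary is 6.0% to 11.4% instead of 5.0%. These figures rest on the assumed capture and on the independent-samples approximation. They show sensitivity and do not estimate what will happen. The point does not depend on any growth over time. It is worth correcting because the remedy is simple and the possible error runs towards the study's conclusion.

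**What to change.** - In Protocol 6.7, in both log instructions (6.7 and 7.3.3) and in any call script, replace the oral-pulse wording with the endpoint definition already in 5.6 and 8.1: systemic corticosteroids by any listed route for worsening asthma, and any rise in daily dose for subjects already on oral steroids.
- Align the medication filter in SAP 6.4 with the same definition. It should cover all systemic routes, including injections not entered under the listed intravenous text strings, and state how a dose increase in a maintenance user is recognised as a course. This step cannot recover events that were never recorded, so the prompts need correcting as well.
- If follow-up is under way, as the SAP's remark about entered data suggests, record the date of change and check earlier periods against the medication and adverse event data already collected. Otherwise the correction could itself create a difference between years. For example, with a true 33% in both years, 95% capture in Year 1 and full capture later would show an apparent worsening of 0.33 − 0.95 × 0.33 = 1.65 points.

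The cost is minor wording changes, a filter revision and a check of existing data. A full retrospective review of source records at all sites would be a larger task and is not needed for this point. The remaining limitation is that events from before the change that appear nowhere in the database stay lost, and the report should say so.
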